10.7 Interim analysis

There is no plan for a formal interim analysis of safety or other secondary endpoints for this study. However, for publication or other purposes, interim data review of clean data will be performed as necessary. At these interim reviews, patient demographics/baseline characteristics, the primary and secondary endpoints as applicable, and all important safety endpoints will be summarized.

No formal report will be issued for these interim data reviews.

10.8 Sample size calculation

The sample size was chosen by the usual criteria of obtaining adequate power for the alternative hypothesis of interest as shown in [Table 14-18](#) of Appendix Q. This hypothesis corresponds to a generally effective treatment across groups and incorporates variation in treatment effects to reflect the realistic expectation that treatment effects may differ by group. In this setting, analytical power calculations are not possible, but the design was simulated to obtain the power of the study as shown in the appendix. The sample sizes shown (minimum of 10 for futility stopping, minimum of 15 for early success and maximum of 30 as a group cap) achieve adequate power for the alternative hypothesis. The simulations included the expected variable accrual by simulating a Poisson process with expected accrual also shown in the appendix.

11 Ethical considerations and administrative procedures

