10.4.3 Evaluation of trial success and futility

The clinical benefit rate will be evaluated for futility and early success by comparing posterior quantities for the rate to pre-specified early stopping criteria. The evaluations are planned to occur after the first 30 patients are dosed for at least 16 weeks or discontinued, then every 13 weeks thereafter until the enrollment closure of the study. An additional CBR evaluation will be performed after the database lock for the primary CSR.

Early Futility

If there is less than 10% probability that the response rate in a group exceeds the historical rate R_g , then the group will stop enrollment early for futility. Formally, enrollment will stop early for futility if:

$$\Pr(\pi_g > R_g) < 0.10.$$

A group is only eligible for early stopping once a minimum of 10 patients has been evaluated for response in that group.

Early Success

If there is at least 95% probability that the response rate in a group exceeds the historical rate, then the group will stop enrollment early for success. Formally, enrollment will stop early for success if:

$$\Pr(\pi_g > R_g) > 0.95.$$

A minimum of 15 subjects will need to be evaluated prior to declaring a group to be efficacious.

Final Analysis

The final analysis will occur when both accrual and follow-up are complete in all groups. If, at the completion of the trial, there is at least 90% probability that the response rate in a group exceeds the historical rate, then the group will be considered a success. Formally if:

$$\Pr(\pi_g > R_g) > 0.90.$$

In addition, a group will be considered as “promising” if:

$$0.80 < \text{Pr}(\pi_g > R_g) < 0.90.$$

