14.17.3.3 Final Analysis

In addition, recall the final analysis will occur when both accrual and follow-up are complete in all groups, or after the database lock for the primary CSR. If, at the completion of the trial, there is at least 80% probability that the response rate in a group exceeds the historical rate, then the group will be considered a success. Formally:

$$\Pr(\pi_g > R_g) > 0.80.$$

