14.17.4.1 Assumptions

Accrual – Two scenarios for the assumed two-year expected accrual are investigated: 1) 10 subjects per group and 2) 5 subjects per group. Note that these are averages, the actual number of available patients is simulated as a Poisson distribution with the specified mean. Also note that the group cap of 30 applies, and thus if the number of available patients in a group exceeds 30, only the first 30 available patients in that group will be enrolled in the study.

Dropouts – We assume no dropouts for the purpose of this simulation.

Control Rates – Table 14-17 shows the assumed control clinical benefit rates for each group.

Table 14-17 Assumed control CBR values used in the simulations.

Tumor Type	Assumed Control Rate (R_g)
Lung LSCL	0.45
Bladder	0.47
Breast	0.50
Colorectal	0.38
GIST	0.50
HNSCC	0.45
Ovarian	0.47
Sarcoma	0.40

We consider four possible scenarios, or possible “truths” in the simulation. These consisted of a null scenario (where the treatment has no effect for any group), an alternative scenario (where the treatment is effective in all groups), a scenario where the treatment was effective in two of the groups, and a scenario where the treatment was effective in half of the groups.

Treatment Rates - The treatment rates for each scenario are shown in the table below. Values identical to the control are shown in bold, while values greater than the assumed control rate are shown in italics.

	Null	Alternative	Two	Half
Lung LSCL	0.45	0.71	0.45	0.45
Bladder	0.47	0.73	0.47	0.47
Breast	0.50	0.75	0.50	0.50
Colorectal	0.38	0.65	0.38	0.38
GIST	0.50	0.75	0.50	0.75
HNSCC	0.45	0.71	0.45	0.71
Ovarian	0.47	0.73	0.73	0.73
Sarcoma	0.40	0.67	0.67	0.67

Simulation Details – For each scenario we simulated 1000 trials. For each interim within each trial, we ran 50,000 MCMC iterations after a 1,000 MCMC iteration burnin.

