14.17.4.2 Results

A total of 8 scenarios were simulated (two accrual scenarios and four possible ‘truths’ for the clinical benefit rate). The probability of group success for each group is provided for each scenario in the below two tables.

Table 14-18 provides the probability of group success for each of the cohort – assuming expected accrual of 10 subjects/cohort and 5 subjects/cohort separately.

Table 14-18 Probability of group success

Two-year expected accrual: 10 subjects/cohort				
Group	Null	Alternative	Two	Half
Lung LSCL	0.158	0.915	0.208	0.305
Bladder	0.131	0.918	0.232	0.322
Breast	0.147	0.909	0.233	0.312
Colorectal	0.138	0.921	0.200	0.276
GIST	0.162	0.921	0.233	0.826
HNSCC	0.139	0.906	0.217	0.834
Ovarian	0.145	0.929	0.786	0.829
Sarcoma	0.135	0.939	0.758	0.852

Two-year expected accrual: 5 subjects/cohort				
Group	Null	Alternative	Two	Half
Lung LSCL	0.132	0.803	0.204	0.258
Bladder	0.140	0.830	0.196	0.265
Breast	0.160	0.807	0.232	0.261
Colorectal	0.135	0.794	0.194	0.278
GIST	0.155	0.826	0.212	0.688
HNSCC	0.140	0.820	0.190	0.657
Ovarian	0.151	0.819	0.587	0.652
Sarcoma	0.139	0.799	0.579	0.667

Entries in bold represent groups where the treatment effect is 0 (e.g. the treatment is ineffective). Thus, entries in bold are type I errors. Entries in italics appear where the treatment is effective, and thus indicate the power of the design.

Generally, type I error is controlled below 0.20 under the null scenario (the borrowing compensates for the multiple interim data reviews) and power is an increasing function of the expected sample size (power is higher in the higher accrual situation across treatment rate scenarios). In the alternative scenario there remains decently high probability of success even in the lower accruing situations. When fewer groups are effective in truth, the scenarios “half” and “two” are harder to discern. Note in any particular trial there should be a mix of high and low enrolling groups, thus some groups may enroll closer to 10 subjects while others may only enroll five. This would produce a power value somewhere between the two tables.

Power is reduced and type I error is inflated when the truth is a mixture of effective and ineffective treatment effects across the groups. Generally power is a function of the sample size.

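### Protocol 10.8 says the powered alternative allows for differing treatment effects, but the simulated alternative is a common odds ratio of 3, with power quoted under a 0.80 success rule

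*Protocol*

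**What the plan says.** Protocol 10.8 chooses the sample size by "obtaining adequate power for the alternative hypothesis of interest as shown in" Table 14-18. It then says that this alternative represents a broadly effective treatment and "incorporates variation in treatment effects to reflect the realistic expectation that treatment effects may differ by group".

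Appendix Q (14.17.1.1 and 14.17.2) defines the treatment effect in group g as the log odds ratio of the response rate against the assumed control rate. Section 14.17.4.1 sets out four scenarios, including "an alternative scenario (where the treatment is effective in all groups"). In the Two and Half scenarios each group is either at its control rate or at the same rate it has under the Alternative. Section 14.17.4.2 comments on these: "Power is reduced and type I error is inflated when the truth is a mixture of effective and ineffective treatment effects across the groups".

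The two parts of the protocol give different final success rules. Appendix Q 14.17.3.3 declares success if "there is at least 80% probability that the response rate in a group exceeds the historical rate". Section 10.4.3 declares it if "there is at least 90% probability that the response rate in a group exceeds the historical rate", and treats 0.80 to 0.90 as promising only. Section 10.8 does not say which rule its power refers to.

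**The concern.** A reader of 10.8 would take the Alternative column as power that already allows for effects differing by tumour type. The model borrows most when groups look alike, so an identical effect in every group is a favourable case for power. If the simulated alternative has no such variation, the sentence describes a robustness that was not tested.

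The same reader, coming from Sections 10.4.2 and 10.4.3, would also assume that the power applies to the 0.90 rule. Both points bear on how to interpret a tumour group that misses the threshold in a signal-seeking trial.

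**Working it through.** **1. The plan's own figures.** Alternative column of Table 14-18:

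- 10 per cohort: (0.915 + 0.918 + 0.909 + 0.921 + 0.921 + 0.906 + 0.929 + 0.939)/8 = 7.358/8 = 0.920.
- 5 per cohort: (0.803 + 0.830 + 0.807 + 0.794 + 0.826 + 0.820 + 0.819 + 0.799)/8 = 6.498/8 = 0.812.
- Mean for the effective groups only: Half 0.835 and 0.666; Two 0.772 and 0.583.

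**2. Effect size per group.** Inputs are the control and Alternative rates in 14.17.4.1. With odds(p) = p/(1 − p), OR = odds(Alternative)/odds(control). The rate at exactly OR 3 is 3·odds(R)/(1 + 3·odds(R)).

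| Group | Control R | Alternative | OR | Rate at OR 3 | Rounded |
|---|---|---|---|---|---|
| Lung | 0.45 | 0.71 | 2.4483/0.8182 = 2.992 | 0.7105 | 0.71 |
| Bladder | 0.47 | 0.73 | 2.7037/0.8868 = 3.049 | 0.7268 | 0.73 |
| Breast | 0.50 | 0.75 | 3.0000/1.0000 = 3.000 | 0.7500 | 0.75 |
| Colorectal | 0.38 | 0.65 | 1.8571/0.6129 = 3.030 | 0.6477 | 0.65 |
| GIST | 0.50 | 0.75 | 3.000 | 0.7500 | 0.75 |
| HNSCC | 0.45 | 0.71 | 2.992 | 0.7105 | 0.71 |
| Ovarian | 0.47 | 0.73 | 3.049 | 0.7268 | 0.73 |
| Sarcoma | 0.40 | 0.67 | 2.0303/0.6667 = 3.045 | 0.6667 | 0.67 |

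All eight match. The SD of the log odds ratio is 0.009, which is rounding. Risk differences run from 0.25 to 0.27 only because control rates and rounding differ.

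**3. Which threshold the table belongs to.** The only final threshold in Appendix Q is 0.80 (14.17.1.1 and 14.17.3.3). Its results section says "Generally, type I error is controlled below 0.20 under the null scenario". The Null column averages 0.144 at both accrual levels. Re-simulating the null at 0.80 gives 0.155 and 0.150.

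**4. Size of the heterogeneity effect.** Two simulations of the Appendix Q model at the 0.80 rule used Dirichlet parameter 2, variance prior IG(3, 0.5), Poisson accrual and the cap of 30. Run A includes the interim looks and reads the 1.82 in the prior for the mean as an SD. Run B has a final look only and reads it as a variance. True log odds ratios vary as Normal(log 3, SD²), and only groups with a true benefit are counted. The SDs are assumptions.

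| Mean power (10 / 5 per cohort) | Run A | Run B |
|---|---|---|
| Common OR 3 | 0.911 / 0.765 | 0.920 / 0.793 |
| SD 0.25 | 0.891 / 0.752 | 0.895 / 0.785 |
| SD 0.50 | 0.851 / 0.727 | 0.864 / 0.759 |

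At SD 0.25 the falls are 2.0 / 1.3 points (A) and 2.5 / 0.8 (B). At SD 0.50 they are 6.0 / 3.8 (A) and 5.6 / 3.4 (B). In Run A, a group fixed at OR 3 while the others vary with SD 0.50 moves only from 0.911 to 0.895 and from 0.765 to 0.744.

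**5. Size of the threshold effect.** With a common OR of 3, changing the final rule from 0.80 to 0.90 gives:

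- Run A: 0.911 to 0.807, and 0.765 to 0.593 (10 and 17 points).
- A separate final-look run: about 0.93 to 0.84, and 0.80 to 0.63 (9 and 17 points).

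**Limits.** At 5 per cohort, Run A is about 5 points below the plan and Run B about 2, so differences are more reliable than levels. Run A did not apply the minimum-enrolment rule, which could matter at a mean of 5.

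**The case against.** The strongest reply is that this is one inaccurate descriptive sentence. Appendix Q prints every assumed rate, shows the Two and Half columns, and says openly that power falls under mixtures. That stands. A reader might infer that the protocol conceals the loss of power, or that Table 14-18 is miscalculated; the documents support neither. The Alternative means are reproduced exactly at 10 per cohort and within 2 points at 5 by the final-look simulation.

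Two and Half do not rescue the sentence, however. They mix OR 3 with no effect, whereas 10.8 describes a generally effective treatment whose size varies. No protocol scenario has effective groups with different effects.

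A reader might also infer that heterogeneity seriously undermines the stated power. It does not, on the assumed range. Run A gives groups with an own OR between 1 and 2 power of 0.61 to 0.70 at 10 per cohort and 0.50 to 0.55 at 5, but any design powered at OR 3 has low power for smaller effects.

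Nor does the finding extend to SAP 9, which repeats the sentence for a different table. The SAP 10.4.1 rates do vary, if mildly: OR 2.85 to 3.59, SD of log odds ratio about 0.08.

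Finally, the 0.80 versus 0.90 conflict is a defect in its own right. It belongs here only because 10.8 quotes power without naming a threshold. Appendix Q also calls its eight cohorts examples, so rerunning that table alone would not give this trial's power.

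**Conclusion.** The statement in 10.8 is wrong as written. On the protocol's own effect scale the powered alternative has no variation beyond rounding, so 0.920 and 0.812 are power for a common odds ratio of 3 under the 0.80 rule. This part rests only on the protocol's tables.

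The practical size is modest for heterogeneity: about 1 to 2 points of average power at SD 0.25 and about 4 to 6 at SD 0.50, both SDs being assumed. It is larger for the threshold: about 0.81 to 0.84 and 0.59 to 0.63 at 0.90, from approximate re-simulation. The correction is worth making because this sentence is the sample-size justification. It does not call the decision rules, the accrual caps or the tabulated figures into question.

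**What to change.** In Protocol 10.8, replace the clause on variation with:

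*The alternative assumes a common odds ratio of about 3 in every example group; power when only some groups benefit is shown in the Two and Half columns of Table 14-18. The Table 14-18 figures apply to a final success threshold of 0.80.*

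Reconcile Sections 10.4.2 and 10.4.3 with Appendix Q. If 0.90 stands, do not cite Table 14-18 as the power under it. Restate power at 0.90 in one of two ways:

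- rerun the table at 0.90; or
- cite Table 2 of SAP 10.4.2, which simulates this trial's expected groups in a section that sets 0.90. Its control rates differ from Appendix Q for the shared groups (breast 0.69 against 0.50, colorectal 0.26 against 0.38, ovarian 0.65 against 0.47), so say which set applies.

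A scenario with varying odds ratios is optional, and SAP 9 needs no change on this point. The cost is two sentences, plus a rerun only if that route is chosen. The downside is a less favourable stated power.

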11.1 Regulatory and ethical compliance

This clinical study was designed, shall be implemented and reported in accordance with the International Conference on Harmonization (ICH) Harmonized Tripartite Guidelines for Good Clinical Practice (GCP), with applicable local regulations (including European Directive 2001/20/EC and US Code of Federal Regulations Title 21), and with the ethical principles laid down in the Declaration of Helsinki.

11.2 Responsibilities of the investigator and IRB/IEC/REB

The protocol and the proposed informed consent form must be reviewed and approved by a properly constituted Institutional Review Board/Independent Ethics Committee/Research Ethics Board (IRB/IEC/REB) before study start. A signed and dated statement that the protocol and informed consent have been approved by the IRB/IEC/REB must be given to Novartis before study initiation. Prior to study start, the investigator is required to sign a protocol signature page confirming his/her agreement to conduct the study in accordance with these documents and all of the instructions and procedures found in this protocol and to give access to all relevant data and records to Novartis monitors, auditors, Novartis Clinical Quality Assurance representatives, designated agents of Novartis, IRBs/IECs/REBs and regulatory authorities as required.

11.3 Informed consent procedures

Eligible patients may only be included in the study after providing written (witnessed, where required by law or regulation), IRB/IEC/REB-approved informed consent. Informed consent must be obtained before conducting any study-specific procedures (i.e. all of the procedures described in the protocol). The process of obtaining informed consent should be documented in the patient source documents. The date when a subject's Informed Consent was actually obtained will be captured in their eCRFs.

Novartis will provide investigators in a separate document with a proposed informed consent form (ICF) that is considered appropriate for this study and complies with the ICH and GCP guideline and regulatory requirements. Any changes to this ICF suggested by the investigator must be agreed to by Novartis before submission to the IRB/IEC/REB, and a copy of the approved version must be provided to the Novartis monitor after IRB/IEC approval.

Women of child bearing potential and fertile males should be informed that taking the study medication may involve unknown risks to the fetus if pregnancy were to occur during the study and agree that in order to participate in the study they must adhere to the contraception requirement for the duration of the study. Women of child bearing potential must agree to adhere to contraception requirement until at least 3 months after the final dose of study treatment. Fertile males must agree to adhere to contraception requirement until at least 3 months after the final dose of study treatment. If there is any question that the patient will not reliably comply, they should not be entered in the study.

11.4 Discontinuation of the study

Novartis reserves the right to discontinue this study under the conditions specified in the clinical study agreement. Specific conditions for terminating the study are outlined in [Section 4.3](#).

11.5 Publication of study protocol and results

Novartis assures that the key design elements of this protocol will be posted in a publicly accessible database such as clinicaltrials.gov. In addition, upon study completion and finalization of the study report the results of this study will be either submitted for publication and/or posted in a publicly accessible database of clinical study results.

11.6 Study documentation, record keeping and retention of documents

Each participating site will maintain appropriate medical and research records for this trial, in compliance with Section 4.9 of the ICH E6 GCP, and regulatory and institutional requirements for the protection of confidentiality of subjects. As part of participating in a Novartis-sponsored study, each site will permit authorized representatives of the sponsor(s) and regulatory agencies to examine (and when required by applicable law, to copy) clinical records for the purposes of quality assurance reviews, audits and evaluation of the study safety and progress.

Source data are all information, original records of clinical findings, observations, or other activities in a clinical trial necessary for the reconstruction and evaluation of the trial. Examples of these original documents and data records include, but are not limited to, hospital records, clinical and office charts, laboratory notes, memoranda, subjects' diaries or evaluation checklists, pharmacy dispensing records, recorded data from automated instruments, copies or transcriptions certified after verification as being accurate and complete, microfiches, photographic negatives, microfilm or magnetic media, x-rays, and subject files and records kept at the pharmacy, at the laboratories, and medico-technical departments involved in the clinical trial.

Data collection is the responsibility of the clinical trial staff at the site under the supervision of the site Principal Investigator. The study eCRF is the primary data collection instrument for the study. The investigator should ensure the accuracy, completeness, legibility, and timeliness of the data reported in the eCRFs and all other required reports. Data reported on the eCRF, that are derived from source documents, should be consistent with the source documents or the discrepancies should be explained. All data requested on the eCRF must be recorded. Any missing data must be explained. An audit trail will be maintained by the system.

The investigator/institution should maintain the trial documents as specified in Essential Documents for the Conduct of a Clinical Trial (ICH E6 Section 8) and as required by applicable regulations and/or guidelines. The investigator/institution should take measures to prevent accidental or premature destruction of these documents.

Essential documents (written and electronic) should be retained for a period of not less than fifteen (15) years from the completion of the Clinical Trial unless Sponsor provides written permission to dispose of them or, requires their retention for an additional period of time because of applicable laws, regulations and/or guidelines.

11.7 Confidentiality of study documents and patient records

The investigator must ensure anonymity of the patients; patients must not be identified by names in any documents submitted to Novartis. Signed informed consent forms and patient enrollment log must be kept strictly confidential to enable patient identification at the site.

11.8 Audits and inspections

Source data/documents must be available to inspections by Novartis or designee or Health Authorities.

11.9 Financial disclosures

Financial disclosures should be provided by study personnel who is directly involved in the treatment or evaluation of patients at the site - prior to study start.

12 Protocol adherence

Investigators ascertain they will apply due diligence to avoid protocol deviations. Under no circumstances should the investigator contact Novartis or its agents, if any, monitoring the study to request approval of a protocol deviation, as no authorized deviations are permitted. If the investigator feels a protocol deviation would improve the conduct of the study this must be considered a protocol amendment, and unless such an amendment is agreed upon by Novartis and approved by the IRB/IEC/REB it cannot be implemented. All significant protocol deviations will be recorded and reported in the clinical study report (CSR).

14.1.1 Measurability of tumor lesions at baseline

All tumor lesions/lymph nodes will be categorized as measurable or non-measurable as follows:

